12.2 Randomization and refusal

The effects of IMR are not yet known. Therefore we think it is ethical to allocate patients randomly to two conditions. After 15-18 months, patients in the CAU group can start IMR. Patients who refuse to participate in the randomization, can still express their preference for one of the two conditions, bur are excluded from the study. This means that they can participate in IMR if they do not wish to participate in the study.

13 Funding

The total budget of the investigation is \leqslant 337.830,- (see Annex 2). The researcher is funded by BavoEuropoort for five years for 2.5 days per week and for five years for one half day per week by the Parnassia Bavo Academy (In total \leqslant 250.000,-). An unconditioned grant of \leqslant 87.830,- for additional costs has been obtained by BavoEuropoort from Janssen-Cilag B.V.

Planned papers

- BMC Article
- English Article about the pilot-study
- Leading article concerning the effectiveness of IMR
- Article on qualitative aspects
- 2 Articles (cross sectional over the baseline data)
- Dutch article about the pilot, if we have time.

Literature

Anthony, WA, Rogers, ES & Farkas, MD (2003). Research on evidence based practices: Future directions in an area of recovery. Community Mental Health Journal, 39, 101-114.

Boevink W. (2002), Samenwerken aan herstel, van ervaringen delen naar kennis overdragen, Trimbos-instituut, Utrecht. (Collaborating on recovery, from sharing of experiences to the transfer of knowledge, Trimbos Institute, Utrecht)

Bogaards M., H. Oosterbaan en [name] (2010), Herstel in een rehabilitatiecentrum, verslag van een onderzoek onder cliënten van het Rehabilitatiecentrum van Bavo Europoort, Onderzoek & Ontwikkeling Bavo Europoort, Rotterdam.

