(Better general recovery, less self-perceived stigma, more self-esteem, achievement of more meaningful goals, more quality of life, more satisfaction, and better social functioning).

3. Improved cost-effectiveness.

4. Design

The design is a randomized controlled trial in which patients are assigned to the experimental condition (IMR) or the control group, after providing written informed consent:

- Group 1. IMR program, offered in a group format + care-as-usual (CAU).
- Group 2. Care-as-usual (CAU)

At randomization, we apply the 'minimization method' (Beller et al 2002). This is a dynamic random allocation method, with the ability to stratify on variables that the outcomes (possibly) influence. We stratify on diagnosis (psychotic disorder yes or no).

The procedure is performed using www.randomizer.org. Using the block-design we ensure that patients end up in the desired ratios in the two conditions (IMR group + CAU vs. CAU).

We have planned three moments of measurement. These moments are

- 1. prior to the randomization
- after the training (in the experimental condition this time may vary depending on the duration of the group, the mean duration of the training in the pilot study was 12.6 months).
 The final (second) moment of measurement for the control group is 12 months after the first moment of measurement.
- 3. The follow-up measurement is 6 months after the second measurement.

5. Study population

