5.3 Sample Size

Based on the effect sizes of the studies of Hasson et al. (2007) with 210 participants (.41, Cohen's d), Levitt et al. (2009) with 104 participants (.36) and Färdig et al. (2011) with 41 participants (.60) we expect a medium effect size of 0.40.

Based on the power analyses with three moments of measurement (mixed models) and equal allocation to experimental and control group, a power of .80, correlation between measures .50, alpha at 0.05 and an effect size of .40, we need to randomize 148 patients, 74 to the experimental condition and 74 to the CAU-group (see Twisk (2003) and Guanghan L. and Kung-Yee L. (1997).

Because of the (conservatively estimated) expected drop-out from treatment in the experimental condition of 50% we choose to allocate more patients to the experimental (IMR-) condition than to the CAU-group (proportions of 3:2). Then we need to randomize 185 patients, 111 patients to the experimental condition and 74 to the CAU-group.

Because we expect a total drop-out in each group from measurements of 8 % we need 80 patients in the control condition and 120 patients in the experimental condition. In total: 200 patients (see Annex 1).

6. Intervention

The average duration of the total IMR-training is 12 months. The IMR-training consists of 11 modules that are given weekly. The first module is given individually. During this individual module the patients decide which goals they want to work on during the program.

Then the patients join an IMR group for the other modules. Each module takes about 3 to 4 sessions of one and a half hours each. The IMR group is guided by two trainers (psychiatric nurses). The trainers received a two-day course in IMR and attend supervision once every two weeks.

The modules are described in the IMR-workbooks, translated into Dutch, which the patients received. If necessary, the original American text is adapted to the Dutch context. The modules are: 1. Recovery Strategies, 2. Practical Facts about Mental Illness, 3. Stress-Vulnerability Model, 4. Building Social Support, 5. Using Medication Effectively, 6. Alcohol and Drugs Use, 7. Reducing Relapses, 8. Coping with Stress, 9. Coping with Problems and Persistent Symptoms, 10. Getting Your Needs Met in the Mental Health System, 11. Health for you.

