8.2.4. Research data

Data on primary, secondary and tertiary outcome measures and the mediating factors will be collected at baseline (before randomization), after the IMR-training (from 9 to 12 months) and during follow-up (after 15 - 18 months). The interviewers will be blind for the (experimental or control) condition of the patient. For the recruitment of participants and data collection, students will be employed.

During the first contact (at baseline) and after the patient has given informed consent, the research interview will take place and the interviews will be conducted. Subsequently randomization will take place. Each assessment will last up to 80 minutes. If desired, the interview will take place on two occasions. The assessments will be done at the location where the patient usually comes. Besides the previously mentioned outcome measures and mediating factors at baseline the following data will also be collected:

- Demographic data: age, sex, living situation, source of income, education level, country of birth of the patient and of his father and his mother.

- Consumption of mental health care: number of outpatient contacts, number of crisis contacts, number of admissions and the number of compulsory admission orders (total and in the last two years) during the past two years before and after moment of measurement 1.
- Psychiatric diagnosis: DSM-IV-TR diagnosis (five axes) according to the clinician. We realize that this is not always reliable, but it is not possible with the resources available to do a standardized diagnostic interview.

The analysis will be based on the intention to treat principle. Data will be collected of patients who drop out of the IMR program. Based on the pilot study, during the IMR intervention, 50 % drop out from IMR is expected. In order to do analyses related to generalizability of the study, the demographic characteristics of all patients who refused to participate will be registered, as well as the characteristics of the patients who drop-out from the study.

The demographic variables, consumption of mental health care and psychiatric illness will be collected by the researcher from the administration of the institution, supplemented by data from the file.

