Given the successful progress of the pilot study it seems that the RCT-study is quite feasible. IMR has become a familiar type of care in the outpatient teams and there is enthusiasm among clinicians and patients. Moreover, there is now an infrastructure for training and supervision of the IMR trainers. Data collection in the pilot study went relatively smoothly. It is difficult to predict the effect of the randomization procedure on the willingness of the patients to participate in the study.

A patient who accepts participation in the control group is essentially ineligible for IMR for a period of 1.5 years. Earlier research showed that about 50% of patients are willing to participate in such an investigation (Henderson et al 2004). Participation often appears very dependent on how clinicians and researchers approach the patient.

For the 85 patients who supposedly will be in an IMR-group in the experimental condition 10 IMR groups need to start in the first year of data collection (baseline measurement). This requires 20 trainers.

The 6 IMR-teams of Bavo Europoort have approximately 60 employees. Everyone is trained in IMR. It is therefore theoretically feasible to undertake the study, and would also make IMR a more explicit component of the care provisions of the group. However, to implement IMR on such a broad scale and to participate in the study is still a challenge for the institution.

We fully anticipate that the enthusiasm of clinicians for this study will lead to the inclusion of the required patient numbers for the study.

11 Time frame

The planning is based on a period of 1 year in which 14 IMR-groups will start and the baseline measurements of all patients will be obtained.

The duration of the 6-IMR groups in the pilot was on average 12.6 months. The following schedule has been assumed that the duration of the groups is 12 months.

Start: April 1th 2011

0 - 15 months (July 2012). Writing definitive protocol, asking permission of medical ethical committee, request of additional grant, training in IMR fidelity-scale, informing clinicians, management, recruitment of students.

15 months (July 2012)- 29 months (September 2013)., training of students, patient recruitment, baseline measurements

17 months (Sept 2012) - 41 months (September 2014). IMR program is offered.

29 months (Sept 2013) - 41 months (September 2014) Second measurements

35 months (February 2014) - 47 months (March 2015). Follow-up measurements

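### Section 12.2 lets control patients start IMR from 15 months, although section 4 puts their follow-up measurement at 18 months and section 10 bars them from IMR for 1.5 years

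*Protocol*

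**What the plan says.** Section 12.2, under the ethical considerations, gives the access rule for the control arm: "After 15-18 months, patients in the CAU group can start IMR".

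Section 4 (Design) sets the measurement schedule. In the IMR arm the second measurement (M2) follows the end of the training, so its timing may vary. For controls it is fixed: "The final (second) moment of measurement for the control group is 12 months after the first moment of measurement". For the third measurement (M3) it says: "The follow-up measurement is 6 months after the second measurement".

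Section 10 (Feasibility) describes what a control patient accepts: "A patient who accepts participation in the control group is essentially ineligible for IMR for a period of 1.5 years".

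Section 8.2.4 gives data-collection times for the trial as a whole, without separating the arms: "after the IMR-training (from 9 to 12 months) and during follow-up (after 15 - 18 months").

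Section 11 gives calendar windows: "15 months (July 2012)- 29 months (September 2013)., training of students, patient recruitment, baseline measurements" and "35 months (February 2014) - 47 months (March 2015). Follow-up measurements".

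Section 9 compares the groups at both the final and the follow-up assessments. Section 8.2.4 says that the analysis follows intention to treat.

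**The concern.** The protocol gives two answers to one operational question: when may a control patient begin IMR? Sections 4 and 10 together imply not before 18 months. Section 12.2, the sentence that grants the access, allows it from 15 months. Staff who follow 12.2 could admit a control to IMR before that patient's M3.

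At stake is the follow-up comparison. Under intention to treat, a control who has begun IMR still counts as CAU at M3. If IMR works, the control arm's M3 scores move towards those of the IMR arm and the difference shrinks.

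**Working it through.** No sample-size or power formula applies. The check is timeline arithmetic.

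**Inputs**
- Control access to IMR: 15 to 18 months (section 12.2).
- Control M2: 12 months after M1, fixed (section 4).
- M3: 6 months after M2 (section 4).
- Bar on IMR for controls: 1.5 years (section 10).
- Trial-wide windows: M2 at 9 to 12 months, follow-up at 15 to 18 months (section 8.2.4).
- Calendar: baseline in trial months 15 to 29, follow-up in trial months 35 to 47 (section 11).

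**Step 1. Where the stated range comes from.** Adding the 6-month interval to the window in 8.2.4 gives 9 + 6 = 15 and 12 + 6 = 18. That reproduces the 15-18 in section 12.2. The lower end needs an M2 at 9 months, and section 4 lets M2 vary only in the IMR arm. For a control it cannot arise.

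**Step 2. Control M3 by section 4.** 12 + 6 = 18 months.

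**Step 3. The bar by section 10.** 1.5 x 12 = 18 months. This agrees with step 2.

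**Step 4. The calendar in section 11.** Last follow-up minus last baseline is 47 - 29 = 18 months. First follow-up minus first baseline is 35 - 15 = 20 months. Neither gives 15. These are trial-wide windows with no control-specific schedule and no bar, so they are consistent with 18 months but do not establish it. Sections 4 and 10 carry the point.

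**Step 5. The gap.** 18 - 15 = 3 months at most between the earliest access under 12.2 and a control's M3.

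**Step 6. What could happen in the gap.** Section 6 gives an average course of 12 months, so 3 months is at most 3/12, a quarter of a course at average pace. This is a ceiling on exposure, not an estimate of bias. Recruitment begins in July 2012, so the first control reaches month 15 in October 2013 (July 2012 + 15 months). Section 11 plans for the trial's 14 groups to start within one year, and IMR is offered from September 2012, so those starts should be over by about September 2013. An early starter would therefore mostly be limited to the individual first module, or would need a group outside the planned set.

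**Step 7. Which contrasts are affected.** Control M2 is at 12 months, before 15, so it is unaffected. Only M3, and any analysis that uses M3, can be.

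**The case against.** The strongest reply is that 12.2 simply means after follow-up. It uses the same range as 8.2.4, section 10 already states the 1.5-year bar, and 18 months lies within the 12.2 range. On this view 12.2 only inherits a mismatch between 8.2.4 and section 4. As a reading of intent, this is probably right. It does not repair the text. Section 12.2 speaks of controls alone, and for them 15 months cannot be the follow-up time under section 4. If 8.2.4 is instead taken to allow a control follow-up at 15 months, then 8.2.4 contradicts section 4. One of them has to change on either reading.

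It is also fair to say that the route to early IMR is narrow, since the planned groups will mostly have started before any control reaches month 15. That limits the likely harm and supports a low severity. Section 12.2 does let patients who refuse randomisation take IMR, but they are excluded from the study, so this says nothing direct about what controls could obtain.

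Two stronger readings are tempting. A reader might infer that the protocol plans to treat controls before their last measurement. The documents do not support that: section 10 says otherwise, and the range is explained by 8.2.4. Nor can it be claimed that access is nowhere tied to M3, because the charts in Annexes 1 and 4 are not shown and might do so. A reader might also infer a calculable loss of power. The protocol gives neither the share of controls who would start early nor the effect of partial IMR. Any power figure would also have to choose an effect for an IMR arm in which section 5.3 expects 50% to drop out of treatment. No such figure is offered here.

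**Conclusion.** The access rule in section 12.2 is wrong as written. Its lower end of 15 months conflicts with the 18-month control follow-up in section 4 and with the 1.5-year bar in section 10. Section 11 agrees with 18 months only indirectly.

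The discrepancy is at most 3 months. If it were acted on, the follow-up contrast would be diluted towards no difference, on the assumption that IMR given to a control acts in the same direction as IMR given in the experimental arm. It would not manufacture a benefit, and it leaves the M2 contrast alone. The amount of dilution cannot be derived from the protocol. Severity is minor: the likely intent is sound and the exposure route is narrow, but the sentence that governs access should not permit contamination of a planned comparison.

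**What to change.** In section 12.2, replace the 15-18 month range with a rule tied to the measurement: CAU patients may start IMR only after their follow-up measurement (M3, planned at 18 months) has been completed or recorded as missed. A separate minimum of 18 months is not needed; it would hold back a control whose M3 was done slightly early and would protect nothing.

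In section 8.2.4, state that for controls M2 is at 12 months and M3 at 18 months, and keep the variable timing for the IMR arm only.

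Nothing else has to be added. Section 8.2.4 already provides for analysis by intention to treat and for recording all treatments in both conditions, so an early start would be visible in the data.

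The cost is two text edits, with no new visits, data or analyses. The one downside is that a control whose M3 runs late waits slightly longer for IMR; allowing access once M3 is recorded as missed keeps that wait from being open-ended.

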Annex 1 Flow chart randomisation of participants

Expected number of patients required for inclusion in the study (using drop-out ratio's of the pilot-study)

(At randomization assignment to experimental and control group in a ratio of 3:2)

Annex 2 Budget Trial Illness Management and Recovery (IMR) at Bavo Europoort

Total budget of the study: € 337.830,-

- 0.8 FTE academic researcher for five years (250,000 Euro)

The researcher is funded by the Parnassia Bavo Group (largely by Bavo Europoort and a smaller part by the Parnassia Bavo Academy).

- (3 x 167 =) 501 interviews:
 - Independent interviewers à € 30,- per interview = 660 x € 30,- = € 19.800, - For patients: 3 interviews (€ 20 + € 25 + € 30 =)€ 75 per patient x 200 = € 15.000,-.

Total for the interviews: € 34.800,-

- Research assistant 2 days per week: about 1000 euros gross per month (scale 45 / 6) including employer's costs: for 3 years: € 42.530,-
- Other costs: € 10.500,-
- o Informationbrochures & posters on the research (€2000,-)
- o Costs of photocopying of the questionnaires (€ 500,-)
- o Traveling expenses of researcher and interviewers € 4000,-
- o Visiting 2 international conferences (2 x € 2000,- =) € 4000,-
- Advise by supervisory committee: PM

Annex 3 Overview Instruments + research contacts per patient

		;	Source of	information	Time	Moment of Measurement		
	dossier	patient	clinician	instrument		M1	M2	МЗ
Demographic data	X					X		
Diagnosis	Х					Х		
Care Consumption	X					Х	Х	Х
Goals		Х		Granholm's Goals Template	15 min	Х	Х	х
Illness management		Х		IMR-scale-patient version	10 min	Х	Х	Х
Illness management			X	IMR-scale clinician version		Х	Х	Х
Coping		X		CSES	10 min	X	X	X
Social Support		X		MSPSS	8 min	X	X	X
Treatment compliance			X	SES		X	X	X
Insight		X		Insight Scale (IS)	7 min	X	X	X
Symptoms		X		BSI	10 min	X	X	X
Addiction		X		item 24 of the ASI	5 min	X	X	X
Recovery		X		MHRM	10 min	X	X	X
Self- Stigma		X		Ismi	10 min	х	Х	Х
Self-Esteem		Х		SERS-SF	7 min	Х	Х	Х
Quality of Life		Х		The EQ-5D	7 min	Х	Х	Х
Satisfaction		Х		Two questions of the ROM	6 min	Х	Х	Х
Social Functioning		х		The SF Scale	15 min	х	х	х
					tot.min.	120	120	120

Annex 4: Flowchart researchprotocol Trial Illness Management and Recovery (IMR) in Bavo Europoort
